9.2.1.1. Suspected Unexpected Serious Adverse Reactions

Lilly has procedures that will be followed for the identification, recording and expedited reporting of suspected unexpected serious adverse reactions (SUSARs) that are consistent with global regulations and the associated detailed guidances.

9.2.2. Adverse Events of Special Interest

The following adverse events of special interest (AESIs) will be used to determine the safety and tolerability of ixekizumab over the range of doses selected for this clinical study.

The AESIs for ixekizumab are:

- cytopenias (leukopenia, neutropenia, and thrombocytopenia)

- clinically significant hepatic events and/or significant elevations in liver function test changes/enzyme elevations (ALT, AST, bilirubin, and alkaline phosphatase)
- infections
- injection site reactions
- allergic reactions/hypersensitivities
- cerebrocardiovascular events
- malignancies
- IBD
- interstitial lung disease
- depression.

Sites will provide details on some of these AEs as instructed on the CRF. Investigators will also educate patients and/or caregivers about the symptoms of allergic/hypersensitivity reactions and will provide instructions on dealing with these reactions (see also Section 7.7.2). A blood sample is to be collected as soon as possible for any patient who experiences an AE of a potential systemic allergic/hypersensitivity reactions during the study as judged by the investigator.

Data on preferred terms associated with cerebrocardiovascular events (defined as death, cardiac ischemic events including MI and hospitalization for unstable angina, hospitalization for heart failure, serious arrhythmia, resuscitated sudden death, cardiogenic shock, coronary revascularization procedure, stroke/transient ischemic attack, peripheral revascularization procedure, peripheral arterial event, and hospitalization for hypertension) will be collected, and these events and any deaths will be adjudicated by an external clinical events committee (CEC) made up of a chairman, 2 cardiologists, and a neurologist.

Data on suspected IBD, as identified by events possibly indicative of ulcerative colitis and Crohn's disease, will be collected and the events will be adjudicated by an external CEC with expertise in IBD.

The role of external CECs is to adjudicate defined clinical events in a blinded, consistent, and unbiased manner throughout the course of a study. The purpose of the CEC for adjudication of cerebrocardiovascular events and the CEC for adjudication of suspected IBD events is to ensure that all reported events are evaluated uniformly by a single group.

9.2.2.1. Allergic Reaction and Hypersensitivity Events

All biologic agents carry the risk of systemic allergic/hypersensitivity reactions. Clinical manifestations of these reactions may include but are not limited to:

- Skin rash
- Pruritus (itching)
- Dyspnea
- Urticarial (hives)
- Angioedema (for example, swelling of the lips and/or tongue)
- Hypotension
- Anaphylactic reaction

Participants with clinical manifestations of systemic allergic/hypersensitivity reactions should be treated per local standard of care. Additional data describing each symptom should be provided to the sponsor in the eCRF.

In case of anaphylaxis or generalized urticaria, additional blood samples should be collected as close as possible to the onset of the event. Follow-up samples should be obtained at the next regularly scheduled visit or 4 weeks after the event, whichever is later. The lab results are provided to the sponsor via the central laboratory or via eCRF.

9.2.3. Complaint Handling

Lilly collects product complaints on investigational products and drug delivery systems used in clinical studies in order to ensure the safety of study participants, monitor quality, and to facilitate process and product improvements.

Patients will be instructed to contact the investigator as soon as possible if he or she has a complaint or problem with the investigational product so that the situation can be assessed.

9.3. Treatment of Overdose

Refer to the IB.

9.4. Safety

9.4.1. Electrocardiograms

For each patient, 12-lead electrocardiograms (ECGs) should be collected locally according to the Schedule of Activities (Section 2). Patients are to be resting for 5 minutes prior to the ECG. It is recommended that patients be in a supine position.

Any clinically significant findings from ECGs that result in a diagnosis and that occur after the patient receives the first dose of the investigational treatment are to be reported to Lilly or its designee as AEs via CRF. Any clinically significant ECG findings prior to receiving drug are to be reported as a preexisting condition.

9.4.2. Vital Signs

For each patient, vital signs measurements are to be conducted according to the Schedule of Activities (Section 2). Vital signs include BP and pulse. Patients are to be resting for a minimum of 5 minutes prior to vital sign collection.

Any clinically significant findings from vital signs measurements that result in a diagnosis and that occur after the patient receives the first dose of study treatment are to be reported to Lilly or its designee as AEs via CRF.

9.4.3. Laboratory Tests

For each patient, laboratory tests (detailed in [Appendix 2](#)) should be conducted according to the Schedule of Activities (Section 2). For those tests that are tested at the central lab, please reference the central laboratory manual for specific instructions.

With the exception of laboratory test results that may unblind the study, Lilly or its designee will provide the investigator with the results of laboratory tests analyzed by a central vendor, if a central vendor is used for the clinical trial.

Any clinically significant findings from laboratory tests that result in a diagnosis and that occur after the patient receives the first dose of investigational product are to be reported to Lilly or its designee as AEs via CRF.

9.4.4. Immunogenicity Assessments

Where local regulations and ERBs allow, blood samples for immunogenicity testing will be collected to determine antibody production against the investigational product as specified in the Schedule of Activities (Section 2).

Immunogenicity will be assessed using a validated assay designed to detect ADAs in the presence of the investigational product at a laboratory approved by the sponsor. Antibodies may be further characterized and/or evaluated for their ability to neutralize the activity of the investigational product. Additionally, a blood sample is to be collected, as soon as possible, for any patient who experiences a potential systemic allergic/hypersensitivity reaction during the study as judged by the investigator. These samples will be tested for immunogenicity and PK, while other laboratory tests may be performed as needed to elucidate the cause of the allergic/hypersensitivity reaction.

Samples will be retained for a maximum of 15 years after the last patient visit for the study, or for a shorter period if regulations and ERBs allow, at a facility selected by the sponsor. The duration allows the sponsor to respond to future regulatory requests related to the investigational product. Any samples remaining after 15 years will be destroyed.

9.4.5. Physical Examination

For each patient, a complete physical examination must be conducted according to the Schedule of Activities (Section 2).

Any clinically significant findings from a complete physical examination that result in a diagnosis and that occur after the patient receives the first dose of study treatment are to be reported to Lilly or its designee as AEs via CRF.

9.4.6. Ocular Examination

At each study visit, investigator or study health care providers will evaluate the patient for any symptoms of anterior uveitis as specified in the Schedule of Activities (Section 2). If the patient develops eye pain or discomfort, eye redness, blurring of vision, or any other symptoms suggestive of anterior uveitis, the patient must be evaluated by an ophthalmologist. The ophthalmologist diagnosis is completed in the CRF.

9.4.7. Chest X-Ray and Tuberculosis Testing

A posterior-anterior view chest X-ray will be obtained, unless the X-ray or results from a chest X-ray obtained within 3 months prior to screening are available. The chest X-ray or results will be reviewed by the investigator or designee to exclude patients with active TB infection.

In addition, patients will be tested at screening and at visits as indicated on the Study Schedule, (Section 2) for evidence of active or latent TB indicated by a positive purified protein derivative (PPD) skin test response (≥ 5 mm induration, between approximately 2 and 3 days after test application, regardless of BCG vaccination history). If the QuantiFERON[®]-TB Gold test or T-SPOT[®] is available and in the judgment of the investigator preferred as an alternative to the PPD skin test for the evaluation of TB infection, either test may be used instead of the PPD test (positive tests excluded) and may be read locally. If the QuantiFERON[®]-TB Gold or T-SPOT[®] test is indeterminate, 1 retest is allowed. If the retest is indeterminate, then the patient is excluded from the study.

Patients with documentation of a negative test result within 3 months prior to baseline (Week 0; Visit 2) do not need a TB screen at Visit 1. Documentation of this test result must include a record of the size of the induration response. A PPD test recorded as negative without documenting the size of induration will result in a retest.

If the PPD test is performed and positive (≥ 5 -mm induration) and the patient has no medical history or chest X-ray findings consistent with active TB, a retest can be performed using a quantiFERON[®]-TB Gold (QTF) or T-SPOT[®].TB (T-SPOT) test.

Note: If retest is done with QTF or T-SPOT, this result will be used to determine eligibility in place of the PPD result. Indeterminate results of either test are to be handled as directed above.

However, patients with a PPD skin test ≥ 5 mm induration or a positive QuantiFERON[®]-TB Gold or positive T-SPOT[®] test at screening but no other evidence of active TB may be rescreened 1 time and may be enrolled without repeating a PPD or QuantiFERON[®]-TB GOLD or T-SPOT[®] test if the following conditions are met:

- after receiving at least 4 weeks of appropriate latent TB infection (LTBI) therapy,
- with no evidence of hepatotoxicity (ALT/AST must remain ≤ 2 times ULN) upon retesting of serum ALT/AST prior to randomization. Such patients must complete appropriate LTBI therapy during the course of the study in order to remain eligible, and
- meet all other Inclusion/Exclusion criteria for participation.

If rescreening occurs within 3 months of the screening chest X-ray, there is no necessity for repeat of chest X-ray for considering enrollment. Patients who have a documented history of completing an appropriate TB treatment regimen with no history of re-exposure to TB since their treatment was completed and no evidence of active TB are eligible to participate in the study. Patients who have had household contact with a person with active TB are excluded, unless appropriate and documented prophylaxis for TB was given.

9.4.8. Quick Inventory of Depressive Symptomatology–Self-Report (16 Items)

For each patient, a QIDS-SR16 assessment will be collected according to the Schedule of Activities (Section 2).

Any clinically significant findings from the QIDS-SR16 assessment that result in a diagnosis and that occur after the patient receives the first dose of study treatment are to be reported to Lilly or its designee as AEs via CRF.

The QIDS-SR16 is a self-administered, 16-item instrument intended to assess the existence and severity of symptoms of depression as listed in the American Psychiatric Association's *Diagnostic and Statistical Manual of Mental Disorders*, 4th Edition (APA 1994). A patient is asked to consider each statement as it relates to the way they have felt for the past 7 days. There is a 4-point scale for each item ranging from 0 to 3. The 16 items corresponding to 9 depression domains are summed to give a single score ranging from 0 to 27, with higher scores denoting greater symptom severity. The domains assessed by the instrument are (1) sad mood, (2) concentration, (3) self-criticism, (4) suicidal ideation, (5) interest, (6) energy/fatigue, (7) sleep disturbance (initial, middle, and late insomnia or hypersomnia), (8) decrease/increase in appetite/weight, and (9) psychomotor agitation/retardation. Additional information and the QIDS-SR16 questions may be found at the University of Pittsburgh IDS/QIDS internet page (<http://www.ids-qids.org/>).

9.4.9. Columbia–Suicide Severity Rating Scale

The C-SSRS (Posner et al. 2007; Columbia University Medical Center [WWW]) is a scale that captures the occurrence, severity, and frequency of suicide-related ideations and behaviors during the assessment period. The C-SSRS must be administered by appropriately trained site personnel. The tool was developed by the National Institute of Mental Health (NIMH) Treatment of Adolescent Suicide Attempters (TASA) trial group for the purpose of being a counterpart to the Columbia Classification Algorithm of Suicide Assessment (C-CASA) categorization of suicidal events. Patients will be assessed according to the Schedule of Activities (Section 2).

The Self-Harm Supplement Form is a one-question form that is completed, at any visit, including baseline visits, that asks for the number of suicidal or nonsuicidal self-injurious behaviors the patient has experienced since the last assessment. For each unique event identified, a questionnaire (Self-Harm Follow-up Form) which collects supplemental information on the self-injurious behavior is to be completed. This information is then documented in the eCRF.

9.4.10. Safety Monitoring

Lilly will periodically review evolving aggregate safety data within the study by appropriate methods.

9.4.10.1. Hepatic Safety Monitoring

If a study patient experiences elevated ALT $\geq 3X$ ULN, ALP $\geq 2X$ ULN, or elevated TBL $\geq 2X$ ULN, liver testing ([Appendix 4](#)) should be repeated within 3 to 5 days including ALT, AST, ALP, TBL, direct bilirubin, gamma-glutamyl transferase, and creatine kinase to confirm the abnormality and to determine if it is increasing or decreasing. If the abnormality persists or worsens, clinical and laboratory monitoring should be initiated by the investigator and in consultation with the study medical monitor. Monitoring of ALT, AST, TBL, and ALP should continue until levels normalize or return to approximate baseline levels. Details for hepatic monitoring depend upon the severity and persistence of observed laboratory test abnormalities.

Additional safety data should be collected via the CRF/electronic data entry/designated data transmission methods if 1 or more of the following conditions occur:

- elevation of serum ALT to $\geq 5X$ ULN on 2 or more consecutive blood tests
- elevated serum TBL to $\geq 2X$ ULN (except for cases of known Gilbert's syndrome)
- elevation of serum ALP to $\geq 2X$ ULN on 2 or more consecutive blood tests
- patient discontinued from treatment due to a hepatic event or abnormality of liver tests
- hepatic event considered to be a SAE

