7.1. Treatments Administered

The Blinded Treatment Dosing Period (Period 2) involves a comparison of ixekizumab 80 mg Q4W to placebo. Ixekizumab treatment regimen will include patients receiving a 160 mg starting dose. All doses are administered via SC injection. [Table RHCH.2](#) shows the treatment regimens.

At baseline (Week 0), all patients will be randomized to a treatment regimen and receive 2 injections. Patients assigned to ixekizumab treatment regimen with 160 mg ixekizumab starting dose will receive 160 mg of ixekizumab as 2 SC injections. Patients assigned to the placebo treatment group will receive 2 SC injections of placebo. During the remainder of the Blinded Treatment Dosing Period (Period 2; Week 0 to Week 16), all patients will receive 1 injection every 4 weeks. Details are provided in [Table RHCH.2](#).

During the Extended Treatment Period (Period 3; Week 16 to Week 52), patients originally assigned to ixekizumab treatment will remain on the same treatment regimen through Period 3. At Week 16, patients originally assigned to placebo will receive ixekizumab 80 mg Q4W with a 160 mg starting dose (as two 80 mg SC injections). To maintain the blind, all patients, regardless of treatment group, will receive 2 SC injections at Week 16. All patients will receive open-label investigational product starting from Week 20.

The investigator or his/her designee is responsible for the following:

- explaining the correct use of the investigational product to the patient/patient caregiver
- verifying that instructions are followed properly
- maintaining accurate records of investigational product dispensing, collection, and administration
- returning all unused medication to Lilly or its designee at the end of the study.

Patients will be instructed to contact the investigator as soon as possible if he or she has a complaint or problem with the investigational product so that the situation can be assessed.

Further instructions and special considerations for the administration of the investigational product are provided in Sections [7.1.1](#), [7.2.1](#), and [7.7.2](#).

Table RHCH.2. Treatment Regimens for Blinded Treatment Dosing Period (Period 2) and Extended Treatment Period (Period 3)

Initial Regimen		Dose Week 0 (Day 1)	Dose Week 4 to Week 12 (Remainder of Period 2)	Dose Week 16	Dose Week 20 to Week 48 (Remainder of Period 3)
	Total injections per patient	2 injections	1 injection Q4W	2 injections	1 injection Q4W

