8.1. Discontinuation from Study Treatment

The reason for and date of discontinuation from study treatment (investigational product) and reason for and date of discontinuation from study participation will be collected for all randomized patients.

8.1.1. *Permanent Discontinuation from Study Treatment*

For any patient permanently discontinuing from study treatment, the investigational product will be withheld, and the patient will complete the ETV and the Post-treatment Follow-up Period (Period 4), as shown in the Schedule of Activities (Section 2).

The following criteria must be followed for discontinuation from study treatment.

- **Subject Decision**
 - the patient or the patient's designee, for example, parents or legal guardian requests to discontinue investigational product.
- **Discontinuation due to a hepatic event or liver test abnormality.** Patients who are discontinued from investigational product due to a hepatic event or liver test abnormality should have additional hepatic safety data collected via electronic data entry.

Discontinuation of the investigational product for abnormal liver tests should be considered by the investigator when a patient meets one of the following conditions, after consultation with the Lilly designated medical monitor:

- alanine aminotransferase (ALT) or aspartate aminotransferase (AST) >8X upper limit of normal (ULN)
 - ALT or AST >5X ULN for more than 2 weeks
 - ALT or AST >3X ULN and total bilirubin (TBL) level >2xULN or international normalized ratio (INR) >1.5
 - ALT or AST >3X ULN with the appearance of fatigue, nausea, vomiting, right upper-quadrant pain or tenderness, fever, rash, and/or eosinophilia (>5%)
 - alkaline phosphatase (ALP) >3X ULN
 - ALP >2.5X ULN and TBL >2X ULN
 - ALP >2.5X ULN with the appearance of fatigue, nausea, vomiting, right upper quadrant pain or tenderness, fever, rash, and/or eosinophilia (>5%)
- Other laboratory tests

- Neutrophil (segmented) counts (see safety monitoring for neutropenia in Section 9.4.10.2):
 - <500 cells/ μL ($<0.50 \times 10^3/\mu\text{L}$ or <0.50 GI/L)
 - ≥ 500 and <1000 cells/ μL ($\geq 0.50 \times 10^3/\mu\text{L}$ and $<1.00 \times 10^3/\mu\text{L}$ or ≥ 0.50 GI/L and <1.00 GI/L) (based on 2 test results; the second test performed within 1 week from knowledge of the initial result)

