Appendix 4. Hepatic Monitoring Tests for Treatment-Emergent Abnormality

Hepatic Monitoring Tests

Hepatic Hematology^a	Haptoglobin^a
Hemoglobin	
Hematocrit	Hepatic Coagulation^a
RBC	Prothrombin Time
WBC	Prothrombin Time, INR
Neutrophils, segmented	
Lymphocytes	Hepatic Serologies^{a,b}
Monocytes	Hepatitis A antibody, total
Eosinophils	Hepatitis A antibody, IgM
Basophils	Hepatitis B surface antigen
Platelets	Hepatitis B surface antibody
	Hepatitis B Core antibody
Hepatic Chemistry^a	Hepatitis C antibody
Total bilirubin	Hepatitis E antibody, IgG
Direct bilirubin	Hepatitis E antibody, IgM
Alkaline phosphatase	
ALT	Anti-nuclear antibody^a
AST	
GGT	Alkaline Phosphatase Isoenzymes^a
CPK	
	Anti-smooth muscle antibody (or anti-actin antibody)^a

Abbreviations: ALT = alanine aminotransferase; AST = aspartate aminotransferase; CPK = creatinine phosphokinase; GGT = gamma-glutamyl transferase; Ig = immunoglobulin; INR = international normalised ratio; RBC = red blood cells; WBC = white blood cells.

^a Assayed by Lilly-designated or local laboratory.

^b Reflex/confirmation dependent on regulatory requirements and/or testing availability..

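### Protocol 9.4.10.1 leaves AST out of both the 3-to-5-day liver-retest trigger and the 5X extra-data trigger, although the discontinuation conditions in 8.1.1 use ALT or AST

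*Protocol*

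**What the plan says.** Protocol 9.4.10.1 opens with the retest condition: "If a study patient experiences elevated ALT $\geq 3X$ ULN, ALP $\geq 2X$ ULN, or elevated TBL $\geq 2X$ ULN". The repeat should follow in 3 to 5 days. The section refers to Appendix 4 for the testing and names ALT, AST, ALP, TBL, direct bilirubin, gamma-glutamyl transferase and creatine kinase. A second list says when additional safety data should be collected. Its transaminase entry is "elevation of serum ALT to $\geq 5X$ ULN on 2 or more consecutive blood tests", with no AST counterpart. That list also covers hepatic discontinuations and hepatic SAEs, whichever enzyme is involved.

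Protocol 8.1.1 says that stopping treatment because of raised liver values "should be considered by the investigator when a patient meets one of the following conditions, after consultation with the Lilly designated medical monitor". Its four transaminase conditions all cover either enzyme. Two matter here: "ALT or AST >5X ULN for more than 2 weeks" and "ALT or AST >3X ULN and total bilirubin (TBL) level >2xULN or international normalized ratio (INR) >1.5". Protocol 9.2.2 counts among the events of special interest "significant elevations in liver function test changes/enzyme elevations (ALT, AST, bilirubin, and alkaline phosphatase".

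Appendix 4 includes "Prothrombin Time, INR" in its coagulation group. Two general provisions also bear on an AST rise. The closing paragraph of 9.4.10.4 directs the investigator to consult the sponsor's physician or scientist about follow-up tests for other special-interest events or abnormal results, and points to Appendix 4. A footnote to Appendix 2 allows unscheduled chemistry, hematology and urinalysis at the investigator's discretion.

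**The concern.** The monitoring step and the decision step use different enzymes. Section 8.1.1 treats ALT and AST alike, but the section that supplies confirmatory data for those decisions reacts to ALT and not to AST. The documents give no reason for the difference.

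The affected pattern is specific: AST at or above 3X ULN while ALT is below 3X and both ALP and TBL are below 2X. The same rise in ALT should bring a repeat panel within days. In AST alone it brings one only if someone chooses to act, with no stated threshold or deadline. At stake is how quickly an AST-led rise is confirmed or dismissed, and whether INR is available for the 8.1.1 condition that uses it. This is a point of patient safety monitoring. Power, type I error and the efficacy comparisons are not involved.

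**Working it through.** The plan gives no calculated figure to reproduce. Its only interval for this step is the 3 to 5 days in 9.4.10.1. The check is how long an AST-led rise waits if only scheduled sampling applies.

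**Inputs (Schedule of Activities, Protocol section 2).** On-treatment chemistry falls on day 28 ± 2 (Week 4) and on days 56, 84, 112, 140, 168, 196, 224, 252, 308 and 364, each ± 4 (Weeks 8, 12, 16, 20, 24, 28, 32, 36, 44 and 52). That is 11 visits and 10 intervals. Screening, baseline, early termination and follow-up visits are left out.

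**Formula.** Shortest gap = (next day − its window) − (previous day + its window). Longest gap = (next day + its window) − (previous day − its window).

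- Week 4 to 8: 52 − 30 = 22 days; 60 − 26 = 34 days.
- The seven 4-week intervals from Week 8 to Week 36: 28 − 8 = 20 days; 28 + 8 = 36 days.
- Week 36 to 44: 304 − 256 = 48 days; 312 − 248 = 64 days.
- Week 44 to 52: 360 − 312 = 48 days; 368 − 304 = 64 days.

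So the wait is within 20 to 36 days in eight of ten intervals and 48 to 64 days in the other two, against 3 to 5 days when ALT reaches 3X.

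**Dosing.** Table RHCH.2 has a column "Dose Week 20 to Week 48 (Remainder of Period 3", with one injection every 4 weeks. The Week 40 dose therefore falls between the Week 36 and Week 44 chemistry samples, and the Week 48 dose between those at Weeks 44 and 52.

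**INR.** After screening, PT/INR is scheduled at Weeks 16, 24, 36 and 52, which is 4 of the 11 chemistry visits. The other 11 − 4 = 7 are Weeks 4, 8, 12, 20, 28, 32 and 44. This count is the same whichever enzyme is raised, so it is background. INR enters the retest only if the reference to Appendix 4 means the full panel, because 9.4.10.1 does not name it.

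**Persistence over two weeks.** The one timed repeat comes at day 3 to 5, which is 14 − 5 = 9 to 14 − 3 = 11 days short of day 14. Later monitoring of a persistent abnormality has no timetable. No day-14 sample is fixed for ALT or for AST.

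**Conditions unaffected.** The other 8.1.1 transaminase criteria (above 8X; above 3X with TBL above 2X; above 3X with symptoms or eosinophilia) can be judged from the same visit's chemistry, hematology and clinical findings.

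**The case against.** The protocol does not ignore AST. It is on every scheduled chemistry panel, in the repeat panel, in 8.1.1 and among the special-interest events. Section 9.2 requires documented review of each laboratory safety report. Section 9.4.10.4 makes consultation on other abnormal results an instruction, whereas the ALT retest is only something that should happen. Section 8.1.1 separately allows stopping for a clinically significant laboratory change in the investigator's opinion. Patients attend at Weeks 40 and 48 and give blood for CRP, so adding chemistry then is easy. The pattern is also narrow, and ALT may have been chosen deliberately as the marker.

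Much of this stands. It means the long intervals arise only when the other routes yield no sample, and that calling the ALT retest mandatory would overstate it. It does not remove the asymmetry: none of these provisions gives an AST threshold or a time limit, and the Appendix 2 footnote does not list coagulation, so that route supplies no INR.

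Three stronger inferences are tempting and are not supported:

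- *The two-week persistence condition is checked late for AST but on time for ALT.* No sample at or after day 14 is timed for either enzyme, so days beyond that mark do not measure a difference between them.
- *The seven chemistry visits without INR are an AST gap.* The schedule is the same for ALT, and adding AST to the trigger does not change it.
- *The SAP loses AST data.* Table RHCH.6.7 defines its elevated hepatic criteria by ALT and bilirubin, but AST has its own elevation and shift analyses in Periods 2 and 3 and its own entry in the patient listing.

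**Conclusion.** The point holds as an inconsistency in safety monitoring. Neither trigger in 9.4.10.1 names AST, while 8.1.1 and 9.2.2 treat it alongside ALT. For the AST-led pattern, early confirmation rests on untimed consultation or discretion. If neither produces a sample, the wait is 20 to 36 days in eight of ten on-treatment intervals and 48 to 64 days in the last two, instead of 3 to 5 days.

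The intervals assume visits within the scheduled windows and no unscheduled testing. The documents do not say how often AST rises without ALT, ALP or TBL, so the number of patients affected is unknown and may be small. The INR benefit of a retest depends on how the Appendix 4 reference is read. This is a cheap improvement worth making, not a flaw that affects the trial's conclusions on efficacy.

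**What to change.** In Protocol 9.4.10.1:

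- Extend the retest trigger to ALT or AST at or above 3X ULN, leaving the ALP and TBL triggers as they are.
- Extend the extra-data trigger to serum ALT or AST at or above 5X ULN, still on at least two consecutive tests.
- Add INR to the tests named for the repeat, so that the INR condition in 8.1.1 can be assessed for either enzyme without relying on a reading of Appendix 4.

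This needs a protocol amendment, which goes to the ethical review boards under Appendix 3.1.2. No new assay is needed: AST is already in the chemistry and repeat panels, and INR is in Appendix 4. The downside is an occasional extra unscheduled sample, including for AST rises of muscle origin. Creatine kinase, already in the repeat panel, helps to identify those.

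Optionally, align the SAP by defining the elevated hepatic criteria in Table RHCH.6.7 with ALT or AST in both places where the term appears (the summary row and the first listing entry). The one practical gain is in Period 4, where that combined row is the table's only hepatic laboratory summary. SAP 6.11.3.1 lets the program safety analysis plan supersede the table, and that plan is not among the documents, so this change is subject to it.
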